Statistical Analysis Plan for the study: "The effects of Menaquinone-7 supplementation in patients with severe coronary calcifications: study protocol for a randomized controlled trial"

SAP authors: [name] ^a, [name] ^b, [name] ^a

Affiliations:

^a Open Patient data Explorative Network (OPEN), Odense University Hospital and Department of Clinical Research, University of Southern Denmark, Odense, Denmark

^b Department of Cardiology, Odense University Hospital, Odense, Denmark

Introduction

This document specifies the planned statistical analysis for the study "The effects of Menaquinone-7 supplementation in patients with severe coronary calcifications: study protocol for a randomized controlled trial" as carried out following the protocol published at ClinicalTrials.gov Identifier: NCT05500443.

Sample size considerations

According to the protocol (1): "We are planning a study of a continuous response variable from independent control and experimental subjects with 1 control per experimental subject. In the AVADEC trial, the mean (standard deviation) two-year CAC progression among 182 men with CAC score ≥ 400 was 380 AU (330 AU) in the placebo group and 288 AU (280 AU) in the intervention group. The joint standard deviation was 311 AU. If this is true in a population of men and women, inclusion of 180 experimental subjects and 180 control subjects are needed to be able to reject the null hypothesis that the population means of the experimental and control groups are equal with probability (power) 0.8. The Type I error probability associated with this test of this null hypothesis is 0.05 (two-sided). Accordingly, 360 subjects are needed. However, to comply with the uncertainty and to account for drop-out of 10%, 400 patients will be included. The sample size is based on two years of treatment."

Randomizations

Randomization is performed by the pharmacy at Odense University Hospital. Based on a computergenerated assignment scheme the tablets will have a random number according to the sequential order.

Statistical principles

All analyses were performed in the intention-to-treat population and as superiority analyses. Two-sided p-values of 0.05 or less were considered to indicate statistical significance and associations and effect estimates will be reported with 95% probability symmetric confidence interval (2.5% to 97.5% quantile).

Practical considerations

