Characteristics (as listed in Table 1 below, numerical characteristics marked with [numerical]) of patients at baseline will be reported separately for the two treatment groups. Characteristics will be reported as

Mean and standard deviation (SD) for numerical characteristics, which are approximately normally distributed in both treatment groups as investigated by normal quantile-quantile plots.

Median and 1st and 3rd quartile (inter quartile range (IQR)) for numerical characteristics, which are not approximately normally distributed in at least one treatment group as indicated by normal quantilequantile plots.

Counts and proportions for categorical characteristics (with categories as specified in Table 1 below).

As the intervention is randomized, no differences between groups will be estimated. Number of missing observations in each group will be specified.

Characteristics	Vitamin K +D group (N=XX)	Placebo group (N=XX)
Age – years [numerical]		
Body-mass index – kg/m ² [numerical]		
Coexisting condition – no (%)		
Diabetes		
Hyperlipidemia		
Hypertension		
• Renal failure, eGFR < 60 mL/min1.73 m ²		
Family history of premature CVD - no (%)		
Smoking status - no (%)		
Active smokers		
Former smokers		
Non-smokers		
Total cholesterol – mmol/L [numerical]		
HDL – mmol/L [numerical]		
LDL – mmol/L [numerical]		
Estimated GFR – ml/min/1.73 m ² [numerical]		
dp-ucMGP – pmol/L [numerical]		
Systolic blood pressure – mmHg [numerical]		
Diastolic blood pressure – mmHg [numerical]		
Medications – no (%)		
ACE inhibitor or ARB		
Beta-blocker		
 Mineralocorticoid-receptor antagonist 		
Antiplatelet therapy		
• NOAC		
Statin therapy		
Baseline CAC score – AU [numerical]		
• 400-999 AU - no (%)		

٠	≥ 1000 AU - no (%)				

ACE denotes angiotensin-converting enzyme, ARB angiotensin-receptor blocker, CAC coronary artery calcification, dp-ucMGP dephosphorylated-uncarboxylated Matrix Gla-Protein, GFR glomerular filtration rate, HDL high-density lipoprotein, LDL low-density lipoprotein, NOAC new-onset anticoagulant

Table 2. Primary outcome and numerical secondary outcomes

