Primary outcome and numerical secondary outcomes will be analyzed by mixed effects linear regression. The mixed effects linear regression models will include a fixed effect for treatment, a fixed effect for time point (baseline, 12 and 24 months) and a fixed effects interaction between treatment and time point. As baseline measurements are obtained before randomization, treatment at baseline will be modelled as a separate common treatment category, constraining baseline measurements to no systematic treatment effect between the two treatment arms, as suggested in literature (6). All mixed effects models will include a random intercept for each included patient. Normality assumptions on residuals and random effects will be evaluated by normal quantile-quantile plots. In case deviations from normality assumptions are detected analyses will be repeated with nonparametric bootstrapping with 1,000 bootstrapping samples (handling individual patients as bootstrapping clusters, and treatment groups as bootstrapping strata).

	Vitamin K+D group	Placebo group	Group difference	
	Mean change from	Mean change	Treatment effect	p-value
	baseline (95 % CI)	from baseline	(95 % CI)	
		(95 % CI)		
Primary outcome				
CAC score (all				
patients)				
Numerical secondary of	utcomes			
CAC score (men)				
CAC score (women)				
CAC score				
(baseline CAC score				
400-999)				
CAC score				
(baseline CAC score				
≥1000)				
AVC score (all				
patients)				
dp-ucMGP				
Quality of life				

All available data will be used in the analyses in Table 2.

Table 3. Secondary outcome on plaque composition

Analyses on change from baseline to 24 months on per patient level in all participants will be carried out similar to Table 2.

	Vitamin K+D group	Placebo group	Group difference	
	Mean change from	Mean change	Treatment effect (95	p-value
	baseline (95 % CI)	from baseline (95	% CI)	
		% CI)		
Plaque volume and c	composition			
Total plaque (mm ³)				
Calcified plaque				
(mm ³)				
Noncalcified plaque				
(mm ³)				
Low-attenuation				
noncalcified plaque				
(<30 HU) (mm³)				

Table 4. Dichotomous secondary outcome and adverse events

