Dichotomous secondary outcomes and adverse events are reported as counts and proportions separately for each treatment group and compared between groups by χ^2 -test if all counts are at least 5, or with Fisher's exact test otherwise. If a patient reported multiple events of the same outcomes, this will be handled dichotomously as experiencing the outcome in the analyses, but the count of such patients will be reported in a parenthesis or footnote to the table.

All available data will be used in the analyses in Table 2, and number of missing observations in each group will be specified.

Event	Vitamin K +D group (N=XX)	Placebo group (N=XX)	p-value
Secondary outcome			
Cardiovascular events (combined) – no (%)			
 Non-fatal myocardial infarction 			
Coronary revascularization			
Cardiac death			
Adverse Events			
Any event – no (%)			
Death – no (%)			
Cardiovascular events (combined) – no (%)			
Myocardial infarction			
Coronary revascularization			
Heart valve surgery			
• Stroke			
 Significant aortic disease (dissection, rupture and surgery) 			
Significant peripheral artery disease			
(thromboembolism and surgery)			
Venous thromboembolism – no (%)			
Severe bleeding – no (%)			
Incident cancer – no (%)			

Table 5. Numerical safety outcomes

Numerical safety outcomes will be analyzed by linear mixed models corresponding to the analyses specified for the primary outcome in Table 2. No subgroup analyses will be performed.

	Vitamin K+D group	Placebo group	Group difference	
	Mean change (95 %	Mean change	Treatment	P-
	CI)	(95 % CI)	effect (95 % CI)	value
hemoglobin				
creatinine (eGFR)				
carbamide				
sodium				
potassium				
calcium				
magnesium				
albumin				
phosphate				
Alkaline phosphotase				
parathyroid hormone				
prothrombin time-				
international				
normalised ratio (PT-				
INR)				

Supplementary Table S1. Stratified analyses of the primary outcome

Analyses of the primary outcome (progression in CAC score) will be repeated stratifying for age (below or above mean age at baseline), diabetes (yes / no at baseline), hypertension (yes / no at baseline), renal failure (yes / no at baseline), statin therapy (yes / no at baseline), and MGP (below / above median). In these analyses, patients will not be stratified by baseline CAC score 400-999 and ≥1000. The same models as for Table 2 will be applied for these analyses.

	Vitamin K +D group	Placebo group		

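### Supplementary Table S1 examines age and baseline MGP only through separate fits below and above the sample mean or median, so it neither tests effect modification nor uses the continuous scale.

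*SAP*

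**What the plan says.** The SAP, under Supplementary Table S1, repeats the primary analysis within strata. Two of the six stratifiers are cut at a sample statistic: age, "stratifying for age (below or above mean age at baseline", and "MGP (below / above median". The other four (diabetes, hypertension, renal failure, statin therapy) are yes/no variables.

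Table 1 lists both variables on a numerical scale: "Age – years [numerical" and "dp-ucMGP – pmol/L [numerical". The latter is the only MGP form in Table 1; Table S1 itself says only MGP.

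On the model, the SAP states for Table S1: "The same models as for Table 2 will be applied for these analyses". The Table 2 model contains treatment, time point and "a fixed effects interaction between treatment and time point". It has no term crossing treatment with a baseline characteristic. Table S1 has one treatment effect and one p-value per stratum, and Figure 4 plots the same stratum estimates. No other analysis in the SAP uses age or MGP as a continuous effect modifier, and no reason is given for the two cuts.

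**The concern.** Readers use a stratified table and forest plot to judge whether the effect differs between kinds of patient. For age and MGP the plan gives two separate answers per variable and nothing that compares them. A small p-value in one half and a large one in the other can arise by chance when the true effect is the same in both.

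If someone does compare the halves, the split has already cost precision. It treats patients just either side of the cut as different and those far apart on the same side as alike. The cut values come from this sample, unlike the fixed thresholds the SAP uses for baseline CAC score (1000) and renal failure (eGFR 60). Another study could apply a published cut value, but that value would still be sample-driven.

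What is at stake is the reading of a supplementary table, not the trial's main conclusion.

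**Working it through.** **Inputs from the SAP, Sample size considerations.** Two-year progression "380 AU (330 AU) in the placebo group and 288 AU (280 AU) in the intervention group"; "The joint standard deviation was 311 AU"; two-sided alpha 0.05; power 0.80; 1:1 allocation; 180 per arm; 400 randomized with 10% drop-out. The SAP gives no figure for effect modification and no distribution for age or MGP, so those are assumptions below.

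**1. The plan's own figure.** Difference 380 − 288 = 92 AU. Per arm: 2 × (1.960 + 0.842)² × 311² / 92² = 179.4, rounded up to 180. Total 360, and 360 / 0.90 = 400. The stated sample size reproduces and is not affected by this point.

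**2. Efficiency of a split.** For a treatment effect that changes linearly with a modifier X, the efficiency of a two-group split relative to a continuous interaction term is the squared correlation between X and the indicator X > cut. For a normal X cut at its mean or median this is 2/π = 0.637, a loss of 36%. On that question 360 patients carry the information of 360 × 0.637 = 229.

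**3. Dependence on the assumed distribution** (2,000,000 draws each; effect linear in X):

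| Distribution of X | Efficiency, median cut | Loss |
|---|---|---|
| Uniform | 0.750 | 25% |
| Normal truncated at ±1.5 SD | 0.701 | 30% |
| Normal | 0.637 | 36% |
| Log-normal, log-SD 0.3 | 0.591 | 41% |
| Log-normal, log-SD 0.5 | 0.517 | 48% |
| Log-normal, log-SD 0.7 | 0.422 | 58% |

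For the three symmetric distributions the mean cut gives the same values. The log-normal rows assume an effect linear in the raw marker. If the effect is linear in log-MGP and log-MGP is normal, the loss is again 36%. Stronger skew (log-SD 1.0) would give 73%, outside the range quoted. If the effect changes in a step near the cut, the split need not be inferior.

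**4. The loss expressed as power.** An interaction with 80% power as a continuous term has, after a split of a normal modifier, power Φ(√0.637 × 2.80 − 1.96) = 0.61. In 4,000 simulated trials of 360 patients the two figures were 78% and 59%. The 80% starting point is illustrative and does not come from this trial.

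**5. What this trial can detect** (SD 311 AU, 360 evaluable, so 90 per arm in each half if the halves are equal):

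- Power for the planned 92 AU within one half: 51%.
- Standard error of the difference in effect between halves: 311 × √(4/90) = 65.6 AU.
- Power for a 92 AU difference between halves: 92 / 65.6 = 1.40, and Φ(1.40 − 1.96) = 0.29.
- Difference needed for 80% power: 65.6 × 2.80 = 184 AU.
- The same dependence on the continuous scale (normal modifier): 1.40 / √0.637 = 1.76, and Φ(1.76 − 1.96) = 0.42.

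The gain is real, from about 29% to about 42%, but the question stays underpowered.

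**The case against.** The strongest defence is that the splits are clearly stated, agree between the text, the rows of Table S1 and Figure 4, and follow rules that do not depend on outcome. Two-row displays are ordinary in supplementary tables. The SAP does not say that Table S1 is meant to test effect modification, so the efficiency figures compare two tests that the plan does not contain. All of this stands. It makes the point an improvement rather than an error, but a prespecified continuous term would guard equally well against a chosen cut.

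A second objection is that a continuous term assumes a form. That also stands: with a threshold near the cut, the split may lose nothing. Choosing a log scale only after seeing skewness would add a data-driven step, so the scale has to be fixed beforehand.

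A reader might go further than the SAP supports in three ways:

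- That the plan discards a third of the information as a matter of fact. The SAP gives neither the distributions nor the form of effect modification, so the figure is conditional.
- That dependence on MGP is the trial's main mechanistic question, or that MGP stands for vitamin K status. The SAP says neither; it lists change in MGP forms as an exploratory endpoint.
- That the investigators are free to choose the cuts. The values are unknown until baseline data are complete, but the rules are fixed.

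**Conclusion.** The point holds as a low-cost improvement to a supplementary analysis. As planned, the Table S1 p-values for age and MGP do not test effect modification, and nothing elsewhere in the SAP recovers the continuous information.

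The loss in any comparison of halves is 36% for a normal modifier with a linear effect, about 25% to 58% across the other distributions considered, and possibly none under a step near the cut. The power figures of about 29% and 42% further assume the planning SD of 311 AU, 360 evaluable patients, equal halves and a normal modifier. A reader might infer that the change would make effect modification detectable or that the main result is in doubt; the figures support neither.

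**What to change.** Add to the Table S1 section that, for age and baseline dp-ucMGP separately, the primary mixed model will be fitted in all patients with modifier x time and arm x time x continuous modifier terms, keeping the common baseline treatment category. Fix the scale in the SAP: age per 10 years, and log2 of dp-ucMGP so that one unit is a doubling. Report the change in the 24-month treatment effect per unit with its 95% CI and the interaction p-value. Confirm that dp-ucMGP is the MGP form meant in Table S1.

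Keep the two-row splits in Table S1 and Figure 4 for display, with a note that their p-values do not compare the strata.

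The cost is two extra model fits, a short addition to the SAP and an assumed linear or log-linear form, which can be checked with a plot. The sample size does not change.

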Data are collected using REDCap hosted by OPEN (Open Patient data Explorative Network, Odense University Hospital, Odense Denmark) with project number OP_1703. Data are analyzed using Stata on OPEN's secure analysis server (OPEN Analyse). A prespecified random seed of 319846 will be used for bootstrapping and/or imputation if these methods are deemed nescessary.

Planned analyses for primary publication

Outcomes

Primary outcome: Main analysis

The primary outcome is the change in coronary artery calcification (CAC) score (numerical) from baseline to 24 month for the full cohort of included patients.

Secondary outcomes

Secondary outcomes are:

- Change in CAC score from baseline to 24 months in men and women, respectively
- Change in CAC score from baseline to 24 months in two pre-specified subgroups (baseline CAC score <1000 and ≥ 1000)
- Change in coronary plaque composition by contrast CT from baseline to 24 months
- Change in calcifications in the aortic valve by non-contrast CT from baseline to 24 months
- Cardiac events (non-fatal myocardial infarction, coronary revascularization, and cardiac death) during the follow-up period
- Change in quality of life from baseline to 24 months.

An exploratory endpoint is:

• Change in MGP with different phosphorylation (p and dp) and carboxylation forms (c and uc).

Safety outcomes

Safety outcomes are:

- Death
- Cardiovascular events (myocardial infarction, coronary revascularization, heart valve surgery, stroke, significant aortic disease (dissection, rupture and surgery) and significant peripheral artery disease (thromboembolisms and surgery)
- Venous thromboembolism including pulmonary embolism
- Bleeding (including intracranial bleeding and hemorrhage associated with a drop in hemoglobin of
 ≥ 2mmol/I)
- Cancer, including solid and hematologic
- Significant deterioration in laboratory measurements (hemoglobin, creatinine (eGFR), sodium, potassium, calcium, magnesium, albumin, phosphate, alkaline phosphatase, parathyroid hormone or prothrombin time-international normalized ratio (PT-INR)).

Dichotomous safety outcomes are evaluated as occurred / not occurred between baseline and 24 months. Numerical safety outcomes are evaluated as change from baseline to 12 and 24 months.

Planned tables and figures and corresponding analyses

Table 1. Characteristics of patients at baseline

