	Mean change from baseline (95 % CI)	Mean change from baseline (95 % CI)	Treatment effect (95 % CI)	P-value
Below mean age				
Above mean age				
No diabetes				
Diabetes				
No hypertension				
Hypertension				
No statin therapy				
Statin therapy				
No renal failure				
Renal failure				
Baseline MGP <				
median				
Baseline MGP >= median				

Supplementary Table S2. Sensitivity analysis: Primary outcome and numerical secondary outcomes with imputation

If more than 5% of observations are missing at 24 months for the main analysis of the primary outcome reported in Table 2 the analysis will be repeated using multiple imputation (assuming missing at random) by mixed effects linear regression with all baseline characteristics included in Table 1 as covariates generating 100 imputations. Results will be reported in a table structured as Table 2.

	Vitamin K+D group	Placebo group			
	Mean change from	Mean change from	Treatment effect	p-value	
	baseline (95% CI)	baseline (95% CI)	(95% CI)		
Primary outcome: N	Primary outcome: Main analysis with imputation				
CAC score (all					
patients)					

Supplementary Table S3. Reasons of abandoning the study

	Vitamin K+D group (n=)	Placebo group (n=)
Excluded after inclusion		
Withdraw informed consent		
Significant comorbidity		
Lost interest		
Experienced side effect		
Personal reasons		
Died		

Figure 1. Enrollment and Randomization of Patients

[figure not shown]

Figure 2. CAC progression according to treatment allocation

CAC score at baseline, 12, and, 24 months will be presented in a graph, where the two treatment groups are plotted with their means and 95% confidence intervals (as obtained from the linear mixed models applied for Table 2). The figure will be presented for all patients (Figure 2A) as well as stratified by the baseline CAC score subgroups 400-999 (Figure 2B) and ≥1000 (Figure 2C). (See mockup figure 2A below, 2B and 2C are similar)

[figure not shown]

Figure 3. Change in plaque volume from baseline to 24 months

Change in plaque volume (mm³) with the 4 groups (total, calcified, noncalcified, low-attenuation noncalcified plaque) from baseline to 24 months follow-up will be presented as a box plot to show difference between the treatment group and placebo group.

[figure not shown]

Figure 4. Forest plot of stratified analyses of the primary outcome

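### Cheap improvement, not an error: the only missing-data sensitivity analysis (Supplementary Table S2) stays within missing at random and cannot probe dropout that depends on the unobserved 24-month CAC score

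*SAP*

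**What the plan says.** - **Main analysis** (SAP, Table 2). A mixed effects linear regression with visits at baseline, 12 and 24 months, a random intercept per patient and a common baseline for the two arms. On missing data it says: "All available data will be used in the analyses in Table 2". Such a model is valid under missing at random, although the SAP does not say so for this model.
- **Sensitivity analysis** (SAP, Supplementary Table S2). It is conditional: "If more than 5% of observations are missing at 24 months", the main analysis is "repeated using multiple imputation (assuming missing at random) by mixed effects linear regression with all baseline characteristics included in Table 1 as covariates", with 100 imputations. A random seed is fixed under Practical considerations.
- **Description of missingness.** For Table 4, the "number of missing observations in each group will be specified". There is also "Supplementary Table S3. Reasons of abandoning the study", which lists reasons by arm, among them comorbidity, side effects and death, but also lost interest and personal reasons. No analysis uses these reasons.
- **Planning values** (SAP, Sample size considerations). Two-year progression was "380 AU (330 AU) in the placebo group and 288 AU (280 AU) in the intervention group" and the joint SD was 311 AU. The total was then set "to account for drop-out of 10%, 400 patients will be included".
- **Sex.** A secondary outcome is "Change in CAC score from baseline to 24 months in men and women, respectively", and Table 2 has a row for each sex. The Table 1 template does not list sex, so the Table S2 covariates, as defined, leave it out.

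**The concern.** A sensitivity analysis for missing data is most useful when it departs from the assumption that the data cannot check. Here that assumption is that, given what has been observed, patients without a 24-month scan would have progressed like those with one. Table S2 enlarges what counts as observed but keeps the assumption in that form. The only other repeat of the main analysis, the bootstrap described for Table 2, deals with non-normality. No delta-adjusted, reference-based or other missing-not-at-random analysis appears.

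The planned dropout of 10% is twice the 5% trigger, so Table S2 will plausibly be run. If it agrees with Table 2, the trial can say that the result is robust to dropout explained by baseline factors. It cannot say how different the dropouts would have to be for the conclusion to change.

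**Working it through.** **Inputs.** From Sample size considerations: difference 380 − 288 = 92 AU; SD 311 AU; two-sided alpha 0.05; power 0.80; 400 randomised, so 200 per arm at 1:1; dropout 10%. Missing shares of 5%, 7%, 15% and 20%, and observed differences other than 92 AU, are assumptions for illustration.

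**The plan's own figure.** n per arm = 2 × (1.96 + 0.842)² × 311² / 92² = 179.4, rounded up to 180. Then 360 / 0.90 = 400. Both figures reproduce.

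**Model for the check.** Two-sample comparison of 24-month change, with the same share m missing in each arm and n = 200 × (1 − m) observed per arm. The benefit is placebo minus active.

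- SE = 311 × √(2/n). The smallest significant difference is 1.96 × SE.
- Adding d AU to the imputed active-arm values lowers the benefit by m × d.
- Simple tipping shift: d = (92 − 1.96 × SE) / m.
- With the extra variance from the shift: solve 92 − m × d = 1.96 × √(2 × 311²/n + d² × m(1 − m)/200).

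| Missing per arm | n observed | SE (AU) | Smallest significant difference (AU) | Simple tipping shift (AU) | With shift variance (AU) |
|---|---|---|---|---|---|
| 5% | 190 | 31.9 | 62.5 | 589 | 546 |
| 10% | 180 | 32.8 | 64.3 | 277 | 268 |
| 15% | 170 | 33.7 | 66.1 | 173 | 169 |
| 20% | 160 | 34.8 | 68.1 | 119 | 118 |

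A simulation with 100 normal imputations per arm, pooled by Rubin's rules, with the observed difference fixed at 92 AU and 60 repeats, agreed with the last column within about 3 AU at 10%, 15% and 20%.

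**Scale.** At 10% missing, active-arm dropouts would have to progress by about 288 + 277 = 565 AU, against 380 AU on placebo.

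**Benchmark: active-arm dropouts progress like placebo (d = 92).** The benefit becomes 92 × (1 − m).
- 10% missing: 82.8 AU, SE 32.8, 95% CI 18 to 147, p about 0.012.
- 20% missing: 73.6 AU, SE 34.9, 95% CI 5 to 142, p about 0.035.

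**Dependence on the observed difference (10% missing, simple formula).** The tipping shift is about 7 AU for an observed 65 AU, 57 for 70, 157 for 80, 277 for 92 and 457 for 110.

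**The other direction.** If the observed benefit were 50 AU (not significant), lowering the imputed active-arm values by (64.3 − 50) / 0.10 = 143 AU would make it significant on the simple formula. The question therefore also has an answer after a non-significant result.

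**Equal shifts.** The same shift in both arms, with equal missingness, cancels. The arms must therefore be shifted separately.

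**The case against.** The best defence is that the SAP has done what many plans do not: it sets a trigger, a method, covariates, a number of imputations and a seed, and it labels the assumption openly. That stands, and it is why this is an improvement and not an error.

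A reader might infer that Table S2 merely repeats the main model's assumption and so tells us nothing. The document does not support that. The main model conditions on arm, visit and observed CAC. Table S2 adds, among others, diabetes, eGFR, smoking, statin therapy and dp-ucMGP. Its missing-at-random condition is weaker, and agreement between the two analyses carries some information.

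A reader might also infer from the reasons in Table S3 that dropout will be informative. The table includes reasons with no evident link to disease, and the SAP gives no evidence that any reason relates to CAC. It makes outcome-related dropout conceivable, no more.

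The defence can also say that the figures show little fragility. At the planned values that is correct. The approximation ignores the 12-month scans, whose use would lower the SE and raise the tipping shifts. The remaining point is that the margin depends on the observed difference and the missing share. Both are unknown now, and the plan would not report the margin.

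Finally, a shift applied only upwards, only in the active arm, and judged only by loss of significance would be a poor remedy. It says nothing after a non-significant result and ignores dropout that hides a benefit. It also leaves open what a 24-month score means for a patient who has died. These objections are right, and the fix is framed to meet them.

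**Conclusion.** The point holds as a low-cost, optional improvement. The plan's one missing-data sensitivity analysis covers dropout explained by measured baseline factors and stops there; nothing else in the SAP examines dropout related to the unobserved 24-month score. There is no contradiction or miscalculation, and the primary estimate and its p-value do not change.

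In size, at 92 AU, SD 311 AU, 200 per arm and 10% missing, the tipping shift in the active arm is about 270 to 280 AU, so the planned result is fairly robust. It falls to about 118 AU at an assumed 20% missing, and towards zero as the observed difference approaches 64 AU at 10% missing. These figures rest on a two-sample approximation with equal missingness in the arms and no gain from 12-month data. They do not show that the trial's result will be fragile.

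**What to change.** Add to the text of Supplementary Table S2:

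1. When the 5% trigger is met, run a delta-adjusted analysis on the same 100 imputations. Shift the imputed 24-month CAC separately in each arm and in both directions over a fixed grid, for example −400 to +400 AU in 50 AU steps. At the planned difference, a 400 AU limit reaches the tipping point at about 7% missing or more (390 AU at 7%, with shift variance).
2. Report the effect and 95% CI at each step. Whether or not the primary result is significant, report the shift at which the conclusion changes, or that none on the grid does so.
3. State whether patients who died are included in the shift.
4. Include sex among the imputation covariates, most simply by adding a row to Table 1.

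The cost is a few sentences, one table row and a loop over imputations already planned. No new data are needed and the sample size does not change. The downside is slightly more analysis and possibly a less favourable statement of robustness.
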